#### 2. Corrected Sample Size Estimate for Length of Stay on the Burn ICU $\geq$ 7 days as **estimated on Admission** but, however, where the **Actual Length of Stay on Burn ICU is** $\geq$ **5.5 days** because of Factors that either not present or not evident or were difficult to quantify at time of admission and consent of the patient.

This sample size calculation is based on the primary statistical procedure for this project which will test the difference in mean pain scores, defined as the average self-report of mean pain score, based on the NAS, during each burn wound care procedures, between individuals randomized to usual care (fentanyl plus saline) and those randomized to the intervention arm (usual care + ketamine). PASS Sample Size (Version 14) was used to perform all sample size calculations eligible individuals over the one-year study duration randomized to control and intervention arms in a 1:1 fashion.

In this situation, where Length of Stay is less than the initially estimated >7 days, we further assume that each individual, will, on average, have a length of stay of 5.5 days on the Burn ICU thus resulting in 11 wound care procedures

performed during hospital stay on the Burn ICU. We determined the minimum sample size for our trial based on 80% power at p = 0.05 to detect a clinically significant difference in mean pain score during the wound care procedure of 2.0 between the control and intervention arms with a standard deviation of 4.0. In addition, to account for the clustered nature of procedures performed on individuals, we have used a sample size inflator (also termed "design effect") of 8.0 as described by the Cochrane manual@ conservatively using an interclass correlation of effects of 0.7 amongst repeated measures of pain scores within each individual and 11 observations per individual.

The required sample size needed to accept the alternative hypotheses that the mean pain care score in the intervention arm decreased by 2 points compared to the control arm at the 0.05 level would require 47 eligible individuals (94 total), our anticipated population of 128 eligible individuals is adequate to show a clinically significant improvement for both intervention arms.

@http://handbook.cochrane.org/chapter\_16/16\_3\_4 approximate analyses\_of\_cluster\_randomized\_trials\_for\_a.htm

Further Explanation For Changing the Estimated Length Of Stay, From The Current >/=7 Days To Proposed >/=5.5 Days: \*To Account For Unpredictable Aspects Of Burn Wounds And Behavior Of Patients With Burn Wounds - See Changes Below. The changes in the next section below are based on the rationale just presented, and are included in the JHU IRB Changes in Research.

#### **Changes Requested:**

- a. Inclusion and length of stay clarifications:
  - The length of stay for our protocol had been set at ≥7 days estimated at time of admission to the burn center. However, the number of days a patient remains in the BURN ICU is highly variable, and dictated by factors difficult to accurately quantify when first admitted. For example, patients leave against medical advice, to seek drugs or alcohol, to return to work, or attend to financial matters. For example, some patients may leave the BURN ICU earlier than was originally estimated due to faster wound healing. Others may proceed to the OR for surgical closure of the wounds prior to 7 days, which typically changes the type and duration of wound care for several days after surgery. The length of ICU stay of others may decrease due to an initial overestimate of wound severity and, hence, a reduced need for close ICU monitoring and a reduced likelihood that the patient would remain in the BICU for 7 or more days.
  - b. Inclusion requirement clarification 1: While retaining the inclusion criteria as estimated LOS  $\geq$ 7 days at time of admission, we request a Change in Research such that the actual minimum number of days spent on the BICU be changed to achieve an average LOS of  $\geq$ 5.5 days. The actual number of wound care sessions is to range from 3-7 days and the range in sessions to be from 3 (1/day for 3 day length of stay) to 14 (2/day days at 2 sessions/day plus 1 session on last day), respectively.

These two ranges (i.e., average LOS  $\geq$ 7 days, average LOS  $\geq$ 5.5 days) were used in estimating two sets of power estimates, sample size and in participant accrual. However, data will be considered on an intent to treat basis for those participants with less than 7 treatment days and less than 14 wound care sessions due to abbreviated stay on ICU, surgery for wound closure that obviates further wound care, or who are discharged early.

C. Inclusion requirement clarification 2: Similarly, there are some patients who are ordered to receive only one dressing change per day rather than the usual two per day, while, rarely, some may be scheduled for 3 wound care sessions on certain days. Data on any participants who are otherwise eligible for the Ketamine Trial but who are ordered to have daily wound care procedures  $\geq 2/day$  or  $\leq 2/day$  will be considered on an intent to treat basis.

Statistical and Database Management Resource: The ICTR is highly regarded for database development incorporating multiple layers of protection. The Director of the ICTR, [name], trained and supervised the Ketamine Team in developing the REDCap database to enter, save, protect and prepare to export for analysis, the data generated in this project. The benefits of the REDCap database include: firewall behind the existing JHU firewall, establishing restricted and unrestricted accessibility modes to ensure IRB protected data remain accessible only to individuals listed on the IRB, compartmentalizing tasks, and running the latest antiviral and anti-hacking software. Data integrity is assured using multiple methods, including utilizing variable definitions and data dictionary (item name and definition, scale, range, out of range and multiple key hit detectors). The complexity of this database is necessitated by the elegant and rigorous study design with 14 repeated measures over 7 consecutive days, which will entail multilevel analysis of time varying and time invariant data. Each variable is coded by day (1-7) and session (1-14), as well as data input quality such as double entry, blinded data collection and data entry, automated checks, auto scoring programs, time lapse between recording and entry, standardized data collection forms, and, enhanced study-specific Manual of Operations for the Safety, Efficacy and Opiate-Sparing Effects of Ketamine for Acute Burn Wound Care Pain in a Setting Analogous to Austere Battlefield Conditions (IRB00089761). The Manual was adapted from a previously developed Manual that was successfully utilized by [name] and his team for Management, Operations, and Evaluating Progress towards Goals. It contains a wealth of detailed information that identify topics covered, specificity of instructions for involved personnel, roles, tasks, timelines, procedures and to ensure adequacy of documentation.

#### **Procedure for Obtaining Informed Consent** Obtaining Consent:

- The patient will be directly admitted from the Emergency Department to the Burn ICU which precludes potential participants from receiving the consent form in advance.

Once the patient is admitted to the Burn ICU, stabilized and oriented to the unit, then the consent designee will approach the eligible participant to obtain his/her consent.

- To identify and confirm the patient's understanding of the study, the "Teach Back Method" will be used and, therefore, will be consistent with JHBMC's patient education policy. Using the Teach Back Method as verification of understanding the consent, ensures that the consent designees will have spent the appropriate amount of time explaining and discussing the study with the patient.
- Unfortunately, those eligible participants who are non-English speaking, have a language barrier, and/or who have a severe hearing impairment, will be unable to enroll in the study despite JHBMC's translator services which are available 24/7. The reason for this is that not all the research tools to be used are available in foreign languages. Valid / reliable translation of standardized psychometric tools is an iterative process that goes well beyond the use of an individual translator. In addition, there may also be policies or sensitivities among some translators that render the burn wound care setting difficult.
- Eligible patients who agree to participate will be registered with the study coordinator once an informed consent form is signed. After eligibility is established, and consent obtained, the study coordinator will assign a *study number* the study number is a sequential number beginning with "1001". Subjects will not begin protocol-specified treatment until eligibility is confirmed and the patient is assigned a study number.

# Tracking eligible-consenting and eligible-not-consenting patients:

Subjects who sign a consent form, but do not initiate protocol treatment for any reason (i.e., subjects who are screen failures), will have study data removed from the database and will not count towards completing our accrual goal of 74-94 subjects. The study coordinator will generate a list - that does not contain PHI - of all burn and age eligible admissions in order to maintain a minimal dataset of variables necessary to characterize the group of study eligible participants who consent with those who do not consent. These data will be used to test the representativeness of the obtained sample with the population of eligible burn admissions who do not consent. These data will enable quantitative statement of generalizability of study findings and to ascertain whether any pertinent subject study characteristic contributed.

Randomization: Group assignment of consecutively admitted and eligible patients providing informed consent will be made according to an a priori, randomly generated, list of 4-digit numbers (numbers will account for non-completers, lost to follow-up, side effects, etc). Participants will be allocated to condition on a random basis in randomly stratified blocks of 2, 4, and 6 to ensure that near-equal group numbers are assigned to each condition at key point throughout the study timeline. Those participants assigned an odd number will be allocated to Group 1 (e.g., Usual Care Plus Saline), and participants assigned an even number will be allocated to Group 2 (e.g., Usual Care Plus Ketamine).

Group assignment will be based on serial admissions meeting study inclusion / exclusion criteria. Randomization as described above is expected to achieve group equivalence in: 1) the first pain severity score obtained using the Numeric Analogue Scale measured during the1st exam prior to the first wound care session in the Burn Center; 2) the TBSA; 3) the need for surgery; 4) the average length of wound care procedures and; 5) "other" variables, including the distribution of baseline symptom severity of acute stress disorder, depression, anxiety, and insomnia (which will all be assessed at study enrollment before the first target dressing change). Baseline data on participants will be recorded, and comparability between study groups will be examined at 25% (n=  $\sim$ 19-24/group) and 50% (n=  $\sim$ 37-47/group) of study completion to assess presence of balancing issues. These same data will also be examined upon study completion (n= 74-94), and their relationship with core outcome targets will be examined. If necessary, their effect will be taken into consideration in planned analyses.

It is anticipated that, given the large sample size, the process of random assignment will ensure adequate balancing across study conditions (Usual Care Condition, Usual Care PLUS Ketamine Augmentation Condition) of potentially confounding variables. That is, for example, participants differing by clinically important variables such as smaller versus larger burns should be equally represented in both groups. The large sample size and the process of random assignment are deemed more than adequate to ensure representation across the two study arms for the differences in important but extraneous variables such as procedure duration and other aspects of wound care, rehabilitation and surgery.

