#### Summary of Medication Dose, Timing, Method:

- a. The Fentanyl loading dose will begin <1 minute prior to each wound care session for both the Usual Care and the Ketamine Augmentation groups.
- b. The drug delivery mechanism for the loading dose of ketamine / placebo, as well as all of the continuous infusions, will be via identical masked / nondescript infusion bags. The ketamine / placebo contents will be delivered at identical volumes and continued for the duration of the wound care session in order to preserve the blind.
- c. The blinded infusion bags will be used to deliver both ketamine and saline and will be prepared and provided by the JHBMC pharmacy ([name]). The pump will be programmed by the JHBC nurse based on the provider's prescription, the randomization schedule and the EPIC order set (displayed in EPIC and on infusion bag label).
- d. Wound Care Protocol and Outcome Protocol Duration:

i. Study / Follow-up Protocol: Eligibility determination (ED); consent procedures; informed consent signed (as soon as possible post-admission to the BICU); randomization; initial wound care protocol soon after consented, (1st wound care optimal); twice daily (preferred) wound care (potential range 0-2 sessions daily: there may be days on which no wound care is performed for various reasons such as dressing type, post op, etc) protocol for 7 consecutive days (potential range 3-7 days); Follow-up 1 day, 1-week and 1-month after last of the 7-day study protocol for a total of 5 weeks or n= 35 days per participant.

ii. Wound Care Study Protocol: Includes pretest assessment, premedication (loading dose), wound care and interim infusion and assessments, posttest assessments. Each wound care procedure including assessments will take approximately 1-2 hours.

ii. Ketamine for Acute Burn Pain During Burn Wound Care Protocol: Twice daily wound care sessions, estimated length of hospitalization on BICU is ≥5 days (range = 3 - 7 days).

2. Burn Center 5-year Average population meeting Key Inclusion Criteria

[name], MSN, Trauma Coordinator, provided the speadsheets with the admissions data. [name] is Trauma Coordinator for the trauma and burns at JHBMC and maintains datasets for the Maryland Institute for Emergency Medical Services Systems (MIEMSS) and the American Burn Association (ABA) Registry and has access to all data from the JHBC entered in these systems.

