# **Participant Dropout**

Dropouts and participants whose wound care ends or changes substantially prior to the anticipated 7day study period will be handled on an intent-to-treat manner in all key analyses with the last data obtained treated as the endpoint for that participant. Reasons for dropout will be recorded and contrasted across group.

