Pharmacy's role in policy decision-making with JHBMC Pharmacy and Therapeutics as well as in preparing the drug and delivery system.

i. JHB Pharmacy and Therapeutics Policy - discussed ketamine for research purposes in clinical setting, arrived at definitive decision in consultation with research pharmacist [name] at JHBMC and the results of her discussion with [name], Director of Interventional Research Pharmacology at JHBMC.

ii. The Ketamine Project team is adding [name] as Co-Investigator on the project for the role and tasks delineated here.

[name] has completed the "Drug Build" for the project. Specifics will be provided. She and [name] (see next) collaborate on the "Order Build" and "Drug Build" to ensure the accurate and timely delivery of study drug to study participants. The study drugs (Ketamine as well fentanyl and saline) will be delivered in plain, nondescript identical delivery system for both study drug and usual care preparations. This allows blinding of provider/prescriber, nurse and patient.

iii. The IRB-approved protocol was presented by [name] at the January 2017

JHMBC Pharmacy & Therapeutics Committee (P&T) meeting for approved use in hospitalized patients. The process for approval of clinical policy versus IRB-approved protocols are through the same committee. Full approval was given at the next P&T Committee meeting by all necessary governing bodies for the use of ketamine in this IRBapproved protocol. The pharmacy and [name] in particular, will continue to work with the Ketamine study team to coordinate provision of study materials in a blinded fashion as described next.

iv. Once the Ketamine Project Management Team identifies and consents a participant, the pharmacist will then randomize the subject based on the schema provided by the ICTR database and statistician as described above. Based on group assignment, the pharmacy will prepare the appropriate medication / placebo / study drug, deliver this to the BICU in identical bags labeled in a blinded fashion. Despite being blinded, the label will include all elements required by law.

[name] Clinical Research Pharmacist Johns Hopkins Bayview Medical Center [name]

[name] has begun the "Order Build" for the order set to be entered in the BICU EPIC. [name], Application Coordinator III Johns Hopkins Health Systems [contact]; IT@jh EPIC

5. Training House Staff and Nursing on Ketamine Protocol

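### The rule that deletes consented patients who never start treatment can remove patients already randomized, contrary to the plan's intent-to-treat handling

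*Combined protocol and SAP*

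**What the plan says.** The deletion rule stands in the protocol's section 4, under the heading on tracking eligible patients who do and do not consent. It applies to "Subjects who sign a consent form, but do not initiate protocol treatment for any reason (i.e., subjects who are screen failures"), and these patients "will have study data removed from the database and will not count towards completing our accrual goal", given there as 74 to 94. The same section keeps a minimal list without identifiers, but its purpose is to compare consenters with non-consenters.

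On the order of events, the Summary of Medication Dose, Timing, Method gives "informed consent signed (as soon as possible post-admission to the BICU); randomization; initial wound care protocol soon after consented". Section 8 (Risks, on the pharmacy's role) says that once the team "identifies and consents a participant, the pharmacist will then randomize the subject based on the schema", and that the pharmacy then prepares the supply for the assigned group.

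On the analysis, the Participant Dropout paragraph of section 7 says that dropouts and patients whose wound care ends or changes early "will be handled on an intent-to-treat manner in all key analyses", with their last data taken as the endpoint. The Changes Requested part of section 4 uses the same label for patients with fewer than 7 days or 14 sessions. No section defines an analysis population.

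**The concern.** Intent-to-treat analysis starts from everyone randomized. A rule that turns on whether treatment began, not on whether the patient had been allocated, can remove patients after randomization and leave no trace of them in the study database. The report could then show a flow in which everyone randomized was treated, without being able to demonstrate it.

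Three things are at stake:

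- **Baseline data and reasons.** The Randomization text in section 4 has acute stress, depression, anxiety and insomnia symptoms assessed at enrolment, before the first study dressing change. A non-starter may therefore already have data. The comparability checks planned at 25%, 50% and completion would describe starters only.
- **Loss by arm.** Reasons for dropout are to be compared across groups, but the deleted patients would not appear in that comparison.
- **Follow-up outcomes.** A patient who had no study session could still be assessed for stress disorder, depression and sleep at follow-up.

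**Working it through.** **1. Sequence.** Three steps can be placed in order from the text.

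- *Eligibility and consent.* Under Procedure for Obtaining Informed Consent, a sequential study number is assigned once both are in place, and treatment may not begin before that.
- *Randomization.* The Randomization text says "Group assignment of consecutively admitted and eligible patients providing informed consent will be made according to an a priori, randomly generated, list". Those randomized are therefore already eligible and consented. Section 8 agrees.
- *First study session.* This comes after randomization in the Summary of Medication Dose, Timing, Method, and after the pharmacy has prepared the assigned supply.

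There is thus an interval, probably short, between allocation and first treatment.

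**2. The rule applied to that sequence.** It has two conditions: consent signed, and treatment not initiated. Randomization status is not one of them. The patients deleted are therefore

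(consented, not randomized) + (randomized, not started).

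The first group can be removed without harm to the randomized comparison. The second belongs to an intent-to-treat population.

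**3. Whether the second group can occur.** Changes Requested lists departure against advice, early surgery, faster healing and over-estimated severity as reasons for short stays. The dosing summary also allows days with no wound care. The plan does not offer these as reasons for never starting, but each could arise between allocation and the first session.

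**4. What a randomized non-starter could contribute.**

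| Outcome | Data from a non-starter |
|---|---|
| Pain during study sessions (Aim 1) | None |
| Requests for extra analgesia during sessions (Aim 2) | None |
| Baseline measures | Yes, if taken before withdrawal |
| Follow-up at 1 day, 1 week and 1 month | Possibly, but timed from the last study session, so no date is defined |

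**5. Numbers.** The sample size has no error that bears on this point. Inputs from the corrected estimate in section 4: difference 2.0, SD 4.0, power 80%, alpha 0.05 (taken as two-sided, since no side is stated), intraclass correlation 0.7, 11 sessions.

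- Design effect = 1 + (11 − 1) × 0.7 = 8.0.
- A two-sample t-test needs 64 per arm. 64 × 8.0 / 11 = 46.5, rounded up to 47 per arm, or 94 in total, as stated.
- In the 7-day case (SD 3.0, 14 sessions) the design effect is 1 + 13 × 0.7 = 10.1. 37 × 10.1 / 14 = 26.7, rounded up to 27 per arm, or 54, as stated.

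Neither figure allows for randomized non-starters. The Data Analysis Plan says only that dropout should be minimal. For scale, **assuming** a fraction d of randomized patients never start, the number randomized to give 94 treated is 94 / (1 − d):

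| Assumed d | 94 / (1 − d) | Randomized (rounded up) | Records deleted |
|---|---|---|---|
| 2% | 95.9 | 96 | 2 |
| 5% | 98.9 | 99 | 5 |
| 10% | 104.4 | 105 | 11 |

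These rates are illustrations; the documents supply none.

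**The case against.** The best defence is that screen failure ordinarily means failure before randomization, and that only such patients were intended. That reading is possible, but the sentence does not carry it: it equates the term with consenting and then not starting, whatever the cause. It is also fair to say that the conflict with intent-to-treat arises by omission. Both places that use the label concern patients whose participation was shortened, and taking the last data as endpoint presupposes some data. No section expressly promises intent-to-treat for patients who were never treated. Even so, the only rule that reaches them is deletion.

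Three stronger conclusions may tempt a reader, and the documents do not support them:

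- *That deletion biases the session-pain result by some amount.* Non-starters have no session scores, so the estimate is the same whether their records are kept or removed. No size in NAS points can be derived.
- *That loss is likely to depend on the arm.* The dosing summary has the nurse program the pump from the randomization schedule, while section 8 has the pharmacist preset it. Those passages need reconciling. They do not show that anyone deciding whether a patient starts knows the allocation: the bags are masked, volumes are identical, and the Blinding section and section 8 keep nurse, patient, assistant and provider unaware. Blinding makes arm-related loss less likely.
- *That the loss is beyond recovery.* The rule removes study data from the database. It does not void the pre-generated allocation list, the pharmacist's role in assignment or the sequential study numbers, from which a count by arm could probably be rebuilt. Reasons and baseline data could not be recovered that way.

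**Conclusion.** The concern holds as a defect in the rule. As written, it permits removal of randomized patients, and this does not fit the intent-to-treat label. The conclusion rests on the stated order of events and on reading the rule literally. If the sponsor meant only patients not yet randomized, the text should say so.

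The likely size is modest. The interval is probably short, assignment is blinded, and the session-based outcomes are unaffected. The number of patients cannot be derived; the illustration gives about 2 to 11 records against 94 treated. The change is worth making because it is cheap and because reasons and baseline data cannot be restored once deleted.

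**What to change.** 1. Limit data removal to consented patients who have not been randomized, and reserve the term screen failure for them.
2. Keep every randomized patient in the database.
3. Report randomized non-starters by arm, with reasons, in a flow table.
4. Define the session-pain set as randomized patients with at least one study session, and label it modified intent-to-treat.
5. Include all randomized patients in the follow-up outcomes where these can be obtained, with a stated reference date (randomization, for example) for those who had no session.
6. State whether randomized non-starters count toward the accrual goal. If they do not, somewhat more patients must be randomized to reach the same number treated; if they do, somewhat fewer will be treated.

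The cost is revised wording, one flow table, a few follow-up contacts and the accrual decision in item 6. It should be settled before any such record is deleted.

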# **Exclusion Criteria:**

- Requiring endotracheal intubation and sedation
- Diminished Level of Consciousness / Cognitive Function:  $MMSE \leq 20$ .
- Diminished Capacity Incapable of providing informed consent (reason(s) to be listed).
- PMH: Insensate to pain in burn wound location (e.g., SCI; peripheral neuropathy)
- Safety: Contra-indication (e.g., potential drug interactions, medical comorbidities)
- 1. Protocol: Study Design, Dosing & Duration:
  - a. Design: Triple blind (nurse, patient, RA) Randomized Controlled, parallel group Trial (RCT):

Group 1: Usual Care plus Saline placebo (IV Fentanyl plus Saline slow infusion administered via programmed pump)

Group 2: Usual Care plus Ketamine augmentation (IV Fentanyl plus low-dose Ketamine slow infusion administered via programmed pump)

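### The arm is coded by whether a four-digit number is odd or even, and the plan neither separates that number from the sequential study number nor keeps the schedule consistently away from blinded staff

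*Combined protocol and SAP*

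**What the plan says.** Four parts of the combined protocol and SAP bear on this.

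- **Procedure for Obtaining Informed Consent.** The study coordinator registers each consenting patient. "After eligibility is established, and consent obtained, the study coordinator will assign a" study number, and "the study number is a sequential number beginning with" 1001. It therefore has four digits.
- **Randomization** (under the heading on tracking consenting and non-consenting patients). Assignment follows an "a priori, randomly generated, list of 4-digit numbers", on a random basis in blocks of 2, 4 and 6. Then comes the key: "Those participants assigned an odd number will be allocated to Group 1", and "participants assigned an even number will be allocated to Group 2". Group 1 is fentanyl plus saline and Group 2 is fentanyl plus ketamine.
- **Section 8, Risks, the item on pharmacy's role.** After consent, the pharmacist randomizes from a schema supplied by the ICTR database and statistician, and sends identical bags with blinded labels to the unit.
- **Handling of the schedule and pump.** In the Summary of Medication Dose, Timing, Method (item c), the burn center nurse programs the pump from the prescription, the randomization schedule and the order set. In the nursing policy in section 8, nurses do not set the doses or rates, and the study pharmacist preprograms the pump. Section 4c (Blinding) names the bedside nurse as one of the three blinded roles.

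**The concern.** An allocation code should tell its reader nothing. A parity code tells the arm to anyone who knows the rule, and here the rule is in the protocol that the study team works from. Two things could go wrong.

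The first is confusion of the two numbers. Both have four digits, both are described as assigned to participants, and the text never says that they are different. Someone implementing the protocol could apply odd/even to the sequential study number and replace the random list with a fixed pattern.

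The second is loss of the blind with the list correctly generated, because a randomization number seen outside pharmacy reveals the arm. Both primary aims are exposed to that knowledge. Pain is self-reported on the NAS to a research assistant. Opiate sparing is counted from requests for additional analgesia, and the PRN section lets nurse and provider judgment enter the decision to give it. No analysis in the plan can undo bias that enters by that route.

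**Working it through.** The plan gives no figure to reproduce here, so the check is on what each reading of the text implies.

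**Inputs.** Odd = Group 1, even = Group 2, and blocks of 2, 4 and 6 (Randomization). Study numbers run in sequence from 1001 (informed consent section). Total N = 94 and 1:1 allocation (corrected sample size estimate). The block sizes are assumed equally likely, because the plan does not state their frequencies.

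**Reading 1: one number.** Apply the parity rule to the sequential study numbers:

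| Study number | Parity | Arm |
|---|---|---|
| 1001 | odd | saline |
| 1002 | even | ketamine |
| 1003 | odd | saline |
| 1004 | even | ketamine |

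Continued to 1094, this gives 47 per arm in strict alternation. The next arm is known for 100% of participants. Issuing the number only after eligibility and consent gives no protection, because the next number in a sequence can be foreseen.

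This reading cannot coexist with the blocked list. A block of 2, 4 or 6 has 2, 6 or 20 equally likely balanced orders, and only one of them is saline-first alternation. Let A(n) be the probability that n consecutive assignments alternate:

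A(n) = (1/3) × [A(n−2)/2 + A(n−4)/6 + A(n−6)/20], with A(0) = 1 and the last block cut off where it overruns n.

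For n = 94 this gives about 3 × 10⁻¹⁹. Random blocks would in effect never produce the sequence that Reading 1 produces every time.

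**Reading 2: two numbers.** If the list is random and unconnected to the study number, the parity of the study number should predict nothing. In 20,000 simulated lists of 94 it matched the arm 50.0% of the time, which is chance. The study number is then harmless.

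The randomization number is not. By the stated rule its parity gives the arm with certainty to anyone who sees it. Someone who also knew all earlier arms, and always guessed the arm that was behind, would name the next arm correctly about 70% of the time in the same simulation, against 50% under full concealment.

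**Who is meant to see the schedule.** The passages side by side:

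| Place | Who sets the pump | From what |
|---|---|---|
| Summary of Medication Dose, Timing, Method, item c | burn center nurse | prescription, randomization schedule, order set |
| Section 8, nursing policy | pharmacy, preset before delivery | study protocol |
| Section 4c, Blinding | not stated | nurse is blinded to contents |

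The first row gives allocation material to a role that the third row says is blinded. The second row contradicts the first. If the schedule shows the randomization number, the first row unblinds the nurse.

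**The case against.** The strongest reply is that the plan already describes sound randomization. The Randomization paragraph specifies a random list and varying blocks, and the odd/even sentence comes right after it, so the number meant is most naturally the list number. Different people and sources are involved: the coordinator issues a sequential number, while the pharmacist randomizes from the statistician's schema after consent. Bags are identical with blinded labels, and nothing in the documents puts the list number on forms, labels or database views.

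Most of this stands, and it rules out three stronger readings that a reader might infer.

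- *That allocation is alternation.* This needs the random list and the blocks, described in the same paragraph, to be set aside. It is a possible misapplication of unclear text, not what the plan prescribes.
- *That the sequential number is the only participant number described.* It is not: the list of four-digit numbers is described as well.
- *That treating fellows and attendings decide eligibility knowing the next arm.* Section 4a names them as consent designees. The text after Table 1 gives the eligibility decision to the study team. Some entry criteria do leave room for judgment, for example "Safety: Contra-indication (e.g., potential drug interactions, medical comorbidities"), but no passage shows that those who apply them can see the list or the next number.

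The reply does not remove the rule itself. The section on pharmacy's role says who randomizes. It does not say that the schema uses codes other than odd/even, or that clinical staff cannot see it, and item c of the medication summary points the other way.

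**Conclusion.** The concern holds in a limited form. The plan prescribes an allocation code whose meaning is published, does not distinguish that code from a second four-digit number, and contradicts itself on whether a blinded nurse works from the schedule.

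The size depends on the reading. If the numbers are merged, the next arm is 100% predictable instead of 50%. If they are kept apart, which is more likely, the arm is readable for each participant whose randomization number is seen outside pharmacy. The documents do not say how many that would be, so the extent of unblinding cannot be estimated. The 70% figure assumes that all earlier arms are known and that block sizes are equally likely; it shows what a leak of past codes would cost concealment, not what is expected to happen.

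This is more than a missing detail, because a stated rule followed as written produces a readable code. It does not establish that selection bias or unblinding will occur.

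**What to change.** 1. Delete the odd/even rule and put non-informative allocation codes on the blocked list.
2. State that the sequential study number from 1001 carries no allocation information and is not the randomization number.
3. State that only the pharmacist holds the schedule, and that each assignment is released only after eligibility and consent are recorded.
4. Reconcile item c of the Summary of Medication Dose, Timing, Method with the nursing policy in section 8 on who programs the pump and from what, so that no blinded role consults the randomization schedule.

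The cost is wording in the protocol and Manual of Operations, plus a re-coded list from the group already building the randomization. It needs no extra patients, visits or staff.
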